#### 9.6.2 **Secondary Analyses**

## 9.6.2.1 Cohort 1: Secondary Safety Analyses

The analyses will focus on safety of the CAB + RPV (oral and injectable) through Weeks 48 and 72 while on treatment.

Analyses will follow specification similar to Week 24 safety for Cohort 1 (Section 9.6.1.2) except that the safety timeframe will be through Weeks 48 and 72.

## 9.6.2.2 Cohort 2: Secondary Safety Analyses

The analyses will focus on safety of the CAB + RPV (oral and injectable) through Week 48 while on treatment OR of CAB LA + RPV LA (injectable) through Week 44 while on treatment.

- Cohort 2a: Analyses will focus on safety of the CAB + RPV (oral and injectable) through Week 48 and will follow specification similar to Week 24 safety for Cohort 1 (Section 9.6.1.2). As supplementary analyses, summary statistics for safety of the study regimen at Week 24 will also be provided.
- Cohort 2b: Analyses will focus on safety of the CAB LA + RPV LA (injectable) through Week 44 and will follow specification similar to Week 24 safety for Cohort 1 (Section 9.6.2.1). As supplementary analyses, summary statistics for safety of the study regimen at Week 20 will also be provided.

## 9.6.2.3 Cohort 1: Drug Tolerability and Acceptability at Weeks 24, 48 and 72

The acceptability and tolerability measures on CAB + RPV (oral and injectable) through Weeks 24, 48, and 72 will be summarized.

Data from social-behavioral assessments and qualitative in-depth interviews will be analyzed to assess acceptability and tolerability. Coding of the transcripts will identify main themes emerging from each of the areas explored in the interview. The qualitative data analysis process will be a descriptive analysis without formal inference, with a more detailed description presented in the qualitative data analysis plan.

## 9.6.2.4 Cohort 2: Drug Tolerability and Acceptability for 48 weeks of CAB + RPV (oral and injectable) or 44 weeks of CAB LA + RPV LA (injectable)

- Cohort 2a: Analyses will focus on CAB and RPV tolerability and acceptability for children who are on 48 weeks of CAB + RPV (oral and injectable) and will follow specification similar to Cohort 1 (Section 9.6.2.3). As supplementary analyses to the Week 48 analysis, summary statistics at Week 24 will also be provided.
- Cohort 2b: Analyses will focus on CAB and RPV tolerability and acceptability for children who are on 44 weeks of CAB LA + RPV LA (injectable) and will follow specification similar to Cohort 1 (Section 9.6.2.3). As supplementary analyses to the Week 44 analysis, summary statistics at Week 20 will also be provided.

#### 9.6.2.5 Cohort 1: Maintenance of Viral Suppression at Weeks 24, 48 and 72

The analyses will summarize plasma HIV-1 RNA data at Weeks 24, 48 and 72 while on treatment, for children on CAB + RPV (oral and injectable)

The overall and per group point and 95% Clopper-Pearson CI estimates of the proportion of children who have HIV-1 RNA  $<50, \ge 50, <200$  and  $\ge 200$  copies/ml, while on treatment, based on the FDA Snapshot Algorithm at visit weeks above will be generated.

The overall and per group point and 95% Clopper-Pearson CI estimates of the proportion of children with confirmed virologic failure while on treatment at visit weeks above will be generated.

As supplementary analyses,

• Overall and per group point and 95% Clopper-Pearson CI estimates of the proportion of children who have (i) HIV-1 RNA <50 copies/ml and (ii) HIV-1 RNA <200 copies/ml while on treatment at visit weeks above will be generated. The proportions will be calculated using non-missing data only.

Any other virology assessments will be described in the Primary SAP.

## 9.6.2.6 Cohort 2: Maintenance of Viral Suppression for Children who are on 48 weeks of CAB + RPV (oral and injectable) or 44 weeks of CAB LA + RPV LA (injectable)

- Cohort 2a: Analyses will focus on maintenance of viral suppression while on treatment for children who are on 48 weeks of CAB + RPV (oral and injectable) and will follow specification similar to Cohort 1 (Section 9.6.2.5). As supplementary analyses to the Week 48 analysis, summary statistics at Week 24 will also be provided.
- Cohort 2b: Analyses will focus on maintenance of viral suppression while on treatment for children who are on 44 weeks of CAB LA + RPV LA (injectable) and will follow specification similar to Cohort 1 (Section 9.6.2.5). As supplementary analyses to the Week 44 analysis, summary statistics at Week 20 will also be provided.

## 9.6.2.7 Cohort 1: Immunologic Response at Weeks 24, 48 and 72

The analyses will summarize immunology data at Weeks 24, 48 and 72 while on treatment for children on CAB + RPV (oral and injectable)

At visit weeks above, the overall and per group median and interquartile range for CD4 count, CD4 percent, CD4 count change from baseline, and CD4 percentage change from baseline will be generated.

## 9.6.2.8 Cohort 2: Immunologic Response for Children who are on 48 weeks of CAB + RPV (oral and injectable) or 44 weeks of CAB LA + RPV LA (injectable)

- Cohort 2a: Analyses will focus on immunologic response while on treatment for children who are on 48 weeks of CAB + RPV (oral and injectable) and will follow specification similar to Cohort 1 (Section 9.6.2.7). As supplementary analyses to the Week 48 analysis, summary statistics at Week 24 will also be provided.
- Cohort 2b: Analyses will focus on immunologic response while on treatment for children who are on 44 weeks of CAB LA + RPV LA (injectable) and will follow specification similar to Cohort 1 (Section 9.6.2.7). As supplementary analyses to the Week 44 analysis, summary statistics at Week 20 will also be provided.

## 9.6.2.9 Cohorts 1 and 2: HIV-1 Genotypic and Phenotypic Resistance for Children with Confirmed Virologic Failure

The number and proportion of children with confirmed virologic failure while on treatment who have HIV-1 genotypic and/or phenotypic resistance at time of virologic failure will be generated. Genotypic and phenotypic resistance data for these children will be summarized.

## 9.6.3 Other Analyses

Long-term washout safety of CAB LA and RPV LA through 48 weeks following permanent treatment discontinuation

Overall and per group point and 95% Clopper-Pearson CI estimates of the proportion of children who: (i) experience at least one drug-related safety failure event, (ii) experience at least one grade 3 or higher adverse event, and (ii) experience at least one SAE through 48 weeks following permanent discontinuation of CAB LA + RPV LA.

Regulatory Submission

For regulatory submission purposes, the analyses will follow specifications in the Primary SAP. Additional analyses/reports and additional analyses specifications for regulatory submission tables, figures, and listings will be specified in a separate document.

#### 9.7 Additional considerations

Special statistical and data analysis considerations may be warranted in the event that the COVID-19 pandemic or other unanticipated occurrences (e.g., natural disasters) affect the conduct of this study and/or the integrity of study data. To the extent possible, any such considerations will be addressed in the Primary SAP.

#### 10 CLINICAL PHARMACOLOGY PLAN

#### 10.1 Pharmacology Objectives

The clinical pharmacology evaluations for this study are designed to determine the pharmacokinetics (PK) of oral CAB + RPV and CAB LA + RPV LA in virologically suppressed children living with HIV-1, two to less than 12 years of age and weighing ≥10 kg and <40 kg to propose weight-band dosing. For the primary and secondary PK objectives, plasma drug concentrations will be quantified. Multiple PK samples will be collected throughout the oral and LA dose intervals to allow determination of PK parameters for CAB and RPV (see Section 10.3 for details).

All PK samples will be registered in the LDMS and shipped to the designated central pharmacology laboratory; refer to the LPC for shipping details, including the timing of shipments.

The pharmacology-related study objectives are as follows.

### Primary - Cohort 1

- To propose an appropriate weight-band dosing regimen for CAB + RPV (oral and injectable).
- To describe the repeat-dose pharmacokinetics of CAB + RPV (oral and injectable) through Week 24.

#### Secondary - Cohort 1

• To describe the repeat-dose pharmacokinetics of injectable CAB LA + RPV LA through Week 48 and through Week 72.

### Secondary - Cohort 2

- To evaluate the repeat-dose pharmacokinetics of CAB + RPV through
  - Weeks 24 and 48 (Cohort 2a: oral followed by injectable)
  - Weeks 20 and 44 (Cohort 2b: injectable only)

#### Other - Cohort 1 and Cohort 2

- To characterize washout PK through 48 weeks following permanent discontinuation of CAB LA + RPV LA
- To characterize PK of different administration methods of CAB + RPV oral formulations through Week 4b (Weight Bands 3, 4, and 5 only)

In Cohort 2a, participants that opted to receive oral lead-in of CAB and RPV will have the option to take the pediatric formulation tablets (CAB DTs and RPV 2.5 mg tablets) either solubilized/dispersed in liquid or by swallowing intact. Therefore, based on the data collected in CRAYON, we will evaluate the differences between the oral administration methods via population PK or other quantitative approach where feasible.

## 10.2 Pharmacology Outcome Measures and Estimands

Table 10. Pharmacology outcome measures

## 10.2.1 Cohort 1 Primary PK Outcome Measures (CAB and RPV)

- PO dosing: Wk. 2 AUC, CL/F, Cmax, Tmax, and pre-dose concentrations (C0)
- LA dosing (starting at Week 4b): Wk. 5 concentrations (C5WK), Wk. 12 concentrations (C12WK), trough concentrations (Ct) prior to IM doses through Wk. 24 and accumulation ratio (Wk. 24:Wk. 8).

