## 5.1.1 Dose Adjustments Due to Changes in Weight Band

Participant weight at the Entry visit will establish the participant's weight band and the assigned oral dosing for the full duration of the oral lead-in phase. Oral dosing will not be adjusted due to weight band changes (increases or decreases in weight) which may occur during the oral lead-in phase.

At each injection visit, participant weight will be assessed prior to administering study product to determine the appropriate weight band and injectable dosing regimen to be administered at that visit. Participants who increase in weight bands will begin the dosing regimen corresponding to their new applicable weight band. However, decreases in weight band will not result in a dose change; participants will remain on the dose regimen of the largest weight band achieved.

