#### 6.1.2 Additional Considerations for a Q8W Injection Schedule

In the event of a dosing regimen modification (see Section 5.1.2), the follow-up visit schedule for each cohort will remain per Sections 6.3 through 6.6 and per Appendix I. However, injections and other select visit procedures, as specified below, will only occur at a Q8W frequency.

Participants newly enrolling into the study on a Q8W injection schedule will have injectable study product administered at the following visits:

- For Cohort 1 (through Week 72) and Cohort 2a (through Week 48 only): Weeks 4b, 8, 16, 24, 32, 40, 48, 56, 64, and 72.
- For Cohort 2b: Entry, Week 4, and at Weeks 12, 20, 28, 36, 44.

When receiving injectable study products on a Q8W schedule, acceptability/tolerability assessments for participants and parents/caregivers and all laboratory evaluations (including urine pregnancy tests and all bloodwork) will be administered on a Q8W schedule and will only take place at injection visits. Non-injection visits for participants on a Q8W injection schedule may be conducted in person or telephonically.

See the IMPAACT 2036 MOP for further details regarding implementation of a dosing regimen modification and associated procedural changes when moving from Q4W to Q8W dosing.

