## 10.2.2 Cohort 1 Secondary PK Outcome Measures (CAB and RPV)

• LA dosing: Ct prior to IM doses at Wk. 48 and Wk. 72 and accumulation ratios (Wk. 48:Wk. 8 and Wk. 72:Wk. 8).

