## 10.2.3 Cohort 2 Secondary PK Outcome Measures (CAB and RPV)

**10.2.3.1** Cohort 2a LA dosing: Ct prior to IM doses through Wk. 24 and Wk. 48 and accumulation ratios (Wk. 24:Wk. 8 and Wk. 48:Wk. 8).

Cohort 2b LA dosing: Ct prior to IM doses through Wk. 20 and Wk. 44 and accumulation ratios (Wk. 20:Wk. 4 and Wk. 44:Wk. 4).

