#### Potential Dose Modification

Dose adjustments for management of individual participant PK target exposures will not occur. In the event of failure with respect to safety and/or PK criteria that are deemed potentially avoidable by lower (or higher) exposure to the study drugs, as judged by the CMC, a dose adjustment will be considered for the applicable weight band. As noted in Section 5.1.2, dosing regimen modifications for each weight band may occur as needed following the Cohort 1 interim analyses and/or based on ongoing reviews of safety, PK, and all other relevant data, and will be implemented across all participants within the applicable weight band group. During the reviews of the data and based on the findings, the protocol team may decide whether to continue with Q4W dosing, move to Q8W dosing, change to a different dose on either the Q4W or Q8W schedule, or gather additional data on the initial Q4W dosing regimen for each weight band.

At the two planned interim analyses, and at any other additional relevant PK analysis, the PK parameters calculated from each individual participant will be used to predict that participant's exposure at Wk. 12 (Cohort 1) or Wk. 8 (Cohort 2b) if they were taking Q8W injections instead of Q4W (via modeling and simulation). Using the *predicted* Q8W dose interval trough concentrations from each participant, the same trough acceptance criteria will be applied as already noted in the protocol above. The same strategy will be used, if needed, during ongoing study PK analyses to assess alternate doses or dose intervals if particular weight-bands do not meet acceptance criteria for either the oral or the LA dosing. In other words, based on the observed PK data from each participant, those participants' predicted exposures on the new dose or dose regimen will be calculated, and the acceptance criteria will be applied to those individual participants' predictions on that new dose or dose interval.

When assessing whether to change the dose interval, if the median of the predicted concentrations from every 8 week dosing meets the LA dosing trough acceptance criteria, new participants in the corresponding Weight Bands may be initiated on every 8 week dosing. Ongoing study participants that enrolled on every 4 week dosing may also transition to every 8 week dosing after their week 24 visit.

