# **Injectable Dosing:**

**Table III: Injection Interval** 

III.A	Q. 4 weeks
III.B	Doses 1 and 2, 4 weeks apart, then Q. 8 weeks

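### Under Q8W dosing the accumulation ratios divide an 8-week trough by a 4-week trough, and after a switch from Q4W the later ratios span two regimens

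*Protocol*

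**What the plan says.** Section 10.2.1 lists among the Cohort 1 primary PK outcomes the troughs "prior to IM doses through Wk. 24 and accumulation ratio (Wk. 24:Wk. 8"). Section 10.2.2 adds "accumulation ratios (Wk. 48:Wk. 8 and Wk. 72:Wk. 8") as secondary outcomes. Section 10.2.3 uses Week 24 and Week 48 over Week 8 for Cohort 2a, and "accumulation ratios (Wk. 20:Wk. 4 and Wk. 44:Wk. 4") for Cohort 2b.

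The primary PK estimand (Table 11) includes treatment at either interval through Week 24 and names this one ratio. Section 10.5.2 computes the ratios from observed troughs and mentions no adjustment for interval or dose.

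The Q8W schedule is defined in Appendix VII, Table III as "Doses 1 and 2, 4 weeks apart, then Q. 8 weeks". Section 6.1.2 places the Q8W injections at "Weeks 4b, 8, 16, 24, 32, 40, 48, 56, 64, and 72" in Cohorts 1 and 2a, and states "For Cohort 2b: Entry, Week 4, and at Weeks 12, 20, 28, 36, 44".

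On changes during treatment, Section 5.1.2 sends children still in oral lead-in straight to Q8W and keeps those past Week 12 on Q4W through Week 24. Under Potential Dose Modification (10.3.1), children enrolled on Q4W "may also transition to every 8 week dosing after their week 24 visit". Section 5.1.1 adds: "Participants who increase in weight bands will begin the dosing regimen corresponding to their new applicable weight band".

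**The concern.** An accumulation ratio compares levels at the same time after a dose, so that only carry-over from earlier doses moves it. The ratios here meet that condition when every interval is four weeks. On Q8W only the first interval is four weeks, and that is the one used for the denominator. The numerator then carries four further weeks of decline, and the ratio mixes accumulation with that decline. For a drug with a short apparent half-life it could read below 1 while drug is building up.

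A second problem arises for children who change interval after Week 24. Their Week 8 trough belongs to one regimen and their Week 48 and 72 troughs to another. A change in maintenance dose on moving up a weight band can shift the ratio in a similar way.

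**Working it through.** **Time since the last injection.** From Section 6.1.2 and the Appendix II target days, counted from the first injection, Q8W injections in Cohort 1 fall on days 0, 28, 84, 140, 196 and so on to 476. The gaps are 28 days once and 56 days thereafter. Cohort 2b has the same pattern from Entry. The Week 8 pre-dose sample (2b: Week 4) is therefore 28 days post-dose. The samples at Weeks 24, 48 and 72 (2b: Weeks 20 and 44) are 56 days post-dose. The Appendix II windows agree: 21 to 31 days for the first gap, then 49 to 59 or 49 to 63 days. This step needs no PK assumption.

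**Size of the mismatch.** The protocol states no numerical ratio to reproduce. As an illustration, take mono-exponential decline with k = ln 2 / half-life and sum the contributions of equal doses. The 200-day half-life is the protocol's adult figure for RPV LA (Section 1.2.2). It gives none for CAB LA, so 28 and 56 days are assumptions.

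- Week 8 trough: exp(-28k)
- Week 24 trough on Q8W: exp(-140k) + exp(-112k) + exp(-56k)
- 8-week level after a single dose: exp(-56k)

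| Half-life | Week 8 trough | Week 24 trough | Protocol ratio 24:8 | 8-week single-dose level | Same-interval accumulation | Factor |
|---|---|---|---|---|---|---|
| 28 d (assumed) | 0.500 | 0.344 | 0.69 | 0.250 | 1.38 | 0.50 |
| 56 d (assumed) | 0.707 | 0.927 | 1.31 | 0.500 | 1.85 | 0.71 |
| 200 d (RPV) | 0.908 | 2.117 | 2.33 | 0.824 | 2.57 | 0.91 |

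The factor is exp(-56k) / exp(-28k) = exp(-28k). It does not depend on dose size or on which later week is the numerator. At Week 72, for example, the 28-day case gives 0.67 against same-interval accumulation of 1.33.

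**Switch after Week 24.** With equal doses and a 56-day half-life, the ratio is 2.81 at Week 24 on Q4W. After the switch, Week 48:Week 8 is 1.59 and Week 72:Week 8 is 1.44. Continued Q4W would give 3.34 at Week 48. The fall from 2.81 reflects the change of regimen.

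**Week 16 as denominator.** On Q8W the Week 16 trough is the first one 56 days post-dose, but it already follows two injections: exp(-84k) + exp(-56k). Week 24:Week 16 is then 0.92, 1.09 and 1.35 at 28, 56 and 200 days. It matches the interval but does not recover 1.38, 1.85 and 2.57.

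**Weight-band changes.** In Table 2 the maintenance doses are identical in Bands 2 and 3, and in Bands 4 and 5. Two moves upward change a dose: Band 2 to 1 (CAB LA 200 to 400 mg, RPV LA 450 to 600 mg) and Band 4 to 3 (RPV LA 300 to 450 mg, CAB LA unchanged).

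**The case against.** Much can be said for the plan. Q4W is the initial Cohort 1 regimen, and on Q4W both samples are 28 days post-dose. Children past Week 12 at a switch stay on Q4W through Week 24, so their primary ratio is protected. Serial troughs through Week 24 are themselves primary outcomes and show build-up directly. Dose decisions rest on oral exposure and the Week 12 (2b: Week 8) LA troughs, not on this ratio. All of this stands and limits the point to Q8W and switched children.

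A reader might infer more than the documents support:

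- That none of the ratios measures accumulation. The interval argument does not touch children on Q4W throughout. Their first dose is larger than later ones (1.5-fold for CAB LA, 1.33- to 1.5-fold for RPV LA), which lowers the ratio, but the intervals match.
- That the RPV ratio would fall below 1. At 200 days it is 2.33 in this model. Values below 1 need a much shorter half-life, which the protocol does not give for either LA product.
- That the Q4W against Q8W gap (2.81 against 1.31 at 56 days) is bias. Most of it is a real regimen difference; the mismatch alone is the factor 0.71.
- That the two regimens will be pooled. No section says so. None separates them for this outcome either, and the estimand covers both.
- That a weight-band move inflates the ratio in full proportion to dose. The child is also heavier, so simple dose-normalisation would not settle it.

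The PK SAP, not shown, may add reporting detail. It cannot change the comparison weeks without departing from outcome measures fixed in the protocol.

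**Conclusion.** The point holds for Q8W and for children who change interval. The mismatch of 56 against 28 days follows from the protocol's own visit schedule. Its size depends on half-life: the ratio is 0.50, 0.71 or 0.91 of same-interval accumulation at 28, 56 or 200 days, under mono-exponential decline, with the first two half-lives assumed. For RPV at the protocol's figure the understatement is about 9%; for a shorter half-life it could be large enough to reverse the reading. The primary Week 24 ratio is affected in children who start on Q8W, and possibly in those with only two injections at a switch, whose handling is left to a later memorandum. Regimen mixing after Week 24 affects the secondary Week 48 and Week 72 ratios. The consequence is a misleading descriptive summary, not a wrong dosing decision.

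**What to change.** Reword 10.2.1 to 10.2.3, Table 11 and the PK SAP as follows.

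- Restrict the accumulation ratio (Week 24, 48 or 72 over Week 8; Cohort 2b Week 20 or 44 over Week 4) to children on Q4W throughout.
- Report Q8W separately and never pool the two regimens.
- For Q8W, do not call a ratio to the Week 8 (2b: Week 4) trough an accumulation ratio. Report the serial 8-week troughs, with Week 24, 48 or 72 over Week 16 (2b: Week 20 or 44 over Week 12) labelled as change relative to the first 8-week trough. State that this denominator follows two injections and is not a single-dose reference.
- Report no ratio across an interval switch; give troughs by regimen instead.
- Flag, or analyse separately, children whose maintenance dose changed with weight band.

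The Week 16 (2b: Week 12) pre-dose samples are already in every sampling schedule in Section 10.3, so no blood draws are added. The cost is smaller groups per ratio and no single accumulation figure for Q8W.

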## 10.2.2 Cohort 1 Secondary PK Outcome Measures (CAB and RPV)

• LA dosing: Ct prior to IM doses at Wk. 48 and Wk. 72 and accumulation ratios (Wk. 48:Wk. 8 and Wk. 72:Wk. 8).

## 10.2.3 Cohort 2 Secondary PK Outcome Measures (CAB and RPV)

**10.2.3.1** Cohort 2a LA dosing: Ct prior to IM doses through Wk. 24 and Wk. 48 and accumulation ratios (Wk. 24:Wk. 8 and Wk. 48:Wk. 8).

Cohort 2b LA dosing: Ct prior to IM doses through Wk. 20 and Wk. 44 and accumulation ratios (Wk. 20:Wk. 4 and Wk. 44:Wk. 4).

#### 10.2.4 Other Outcome Measures

- CAB and RPV concentrations 8 to 48 weeks following final IM dose
- PO dosing: Wk. 2 AUC, CL/F, Cmax, Tmax, and pre-dose concentrations (C0) by administration mode

Table 11.
Pharmacology Estimands

	Primary PK Estimand (Cohort 1)
A primary question of interest	What is the PK profile of repeat-dose pharmacokinetics CAB+RPV (~4 weeks of oral lead-in followed by ~20 weeks of injectable) (orally lead-in followed by injectable through Week 24) in virologically suppressed children living with HIV-1, two to less than 12 years of age?
Attributes	
Population	Virologically suppressed children living with HIV, 2 to less than 12 years of age, who received CAB + RPV through Week 24.
Endpoints/ Variables	
 
o PO: Wk. 2 AUC, CL/F, Cmax, Tmax, and pre-dose concentrations (C0)
 
o LA: C5WK, C12WK, and Ct prior to IM doses through Wk. 24 and accumulation ratio (Wk. 24:Wk. 8).
 

	As shown in Table 10
Treatment condition	Oral CAB + Oral RPV once daily through Week 4, followed by LA CAB + LA RPV Q4W or Q8W through Week 24 (see Schema on treatment details).

Intercurrent events (ICE)	
 
o Premature permanent discontinuation of study drugs for any reasons (e.g., death) during treatment phase through Week 24 has impact on PK assessment. While-on-treatment strategy will be applied to address this ICE.
 
o Use of prohibited medications that potentially has significant impact on PK concentrations per clinical pharmacologist will also be addressed by 'while-on-treatment strategy'.
 

Population- level summary	Summary statistics e.g., arithmetic mean, geometric mean, median, standard deviation, minimum, maximum, and coefficient of variation, 90% confidence interval, etc.

